3.1 Primary Endpoints

1) To estimate the percentage of patients who can safely omit surgery, defined as the percentage of patients at two years after end of CRT who have not had surgery and who are in CR (no detectable local disease)

2) The percentage of patients who have local failure at two years, where local failure is defined as surgically unsalvageable disease.

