4.4 Treatment withdrawal criteria

- a) Patient decision to withdraw from trial and proceed to surgery
- b) Following registration, disease (that has not yet achieved a modified Mandard tumour regression grade 1 or 2; Appendix 10.2) that shows stable disease over 2 consecutive MRI scans, 4 weeks apart.

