6.2 Overall Survival

This will be measured from date of entry into study to date of death from any cause. Patients remaining alive or lost to follow up will be censored at the date of last follow up.

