8.0 STATISTICAL CONSIDERATIONS

Analysis methods

All time-to-event endpoints will be measured from the end date of chemoradiotherapy, and calculated using Kaplan-Meier methods. The final analysis will be carried out when all patients have had at least 2 years follow-up. An additional overall survival analysis may be carried out after all patients have had at least 10 years follow-up. **Patients who have not yet experienced the event in question will be censored at date of last follow-up**.

Primary endpoints

Since all patients will have at least two years complete follow-up, the percentage of patients in continued response without surgery at two years, and the percentage of patients with local failure at two years, will be calculated as percentages of all patients, with exact 95% binomial confidence intervals.

Secondary endpoints

Time to distant disease will be measured as the time to the first diagnosis of lymph node or other distant disease, confirmed via PET/CT, MRI, CT or pathology.

Time to maximal tumour response will be defined as follows: for patients who achieve CR, it is the time until first recorded MRI scan with tumour grade T0. In patients where this has not happened, it will be the time to the first of two consecutive MRI scans which show the same modified Mandard regression grading (or the first of two consecutive scans in which the second scan shows an increased Mandard regression grade). Patients with a continuing reduction in Mandard grade at the time of analysis will be censored at the date of last scan..Patients who opt for surgery or withdraw for other reasons before recorded maximal response will be censored at date of last scan.

Time to local regrowth will be measured as the time until the first recorded increase in Mandard grade, on MRI. Patients with continued stable disease or complete response will be censored at date of last MRI scan. Patients who opt for surgery or withdraw for other reasons before recorded local regrowth will be censored at date of last scan.

Of all patients who had surgery for progression of local disease, the percentage with positive margins will be calculated, with an exact 95% confidence interval. The percentage who had negative margins and had their sphincters preserved will also be calculated with an exact 95% confidence interval

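### The two-year local-failure percentage assumes complete follow-up, so a patient whose local status is unknown can only help the safety co-primary endpoint to pass

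*Protocol*

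**What the plan says.** Section 3.1 of the protocol defines the second primary endpoint as follows: "The percentage of patients who have local failure at two years, where local failure is defined as surgically unsalvageable disease". In section 8.0 the analysis of both primary endpoints opens with "Since all patients will have at least two years complete follow-up" and concludes that they "will be calculated as percentages of all patients, with exact 95% binomial confidence intervals". On timing, the same section says: "The final analysis will be carried out when all patients have had at least 2 years follow-up".

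The sample-size text in 8.0 sets the decision rule. It uses a single-stage exact design with one-sided 5% significance, an unacceptable failure rate of 15% and an expected rate of at most 5%. The trial passes this endpoint with no more than 4 failures among 59. Planned recruitment is 39 plus 20, which is 59.

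Elsewhere the protocol expects some patients to leave:

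- Section 4.4 lists "Patient decision to withdraw from trial and proceed to surgery".
- Section 6.2, for overall survival: "Patients remaining alive or lost to follow up will be censored at the date of last follow up".
- Section 8.0, for time to local regrowth: "Patients who opt for surgery or withdraw for other reasons before recorded local regrowth will be censored at date of last scan".

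The time-to-event endpoints therefore have a rule for patients who are no longer observed. The local-failure percentage has none.

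**The concern.** Local failure is an adverse event that somebody has to see and record. With a denominator of all patients and a numerator of recorded failures, an unobserved patient counts in practice as a non-failure. Missing outcomes then move the result in one direction only, towards passing.

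The other primary endpoint behaves the opposite way. A patient not known to be in complete response without surgery cannot count as a success, so missing data make that endpoint harder to pass. The problem is confined to local failure, the endpoint that is meant to show that deferring surgery is safe. What is at stake is whether the stated one-sided 5% error rate holds for that claim.

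**Working it through.** **Inputs from the protocol (8.0):** n = 59; pass if X ≤ 4; unacceptable rate 15%; expected rate 5%; one-sided level 0.05. The protocol gives no loss rate, so the loss rates below are assumptions.

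**1. Reproduce the design.** With X ~ Bin(59, p):

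- Type I error: P(X ≤ 4; p = 0.15) = 0.0469.
- Power: P(X ≤ 4; p = 0.05) = 0.828, against the stated 80%.
- With 58 patients, the largest cut-off that keeps the error at or below 0.05 is 3, and power is 0.670. In a scan of n from 50 to 66, 59 is the smallest n that meets both targets.

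The stated design is correct when every outcome is known.

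**2. A fixed number m of patients unobserved, pass rule still ≤ 4.** Failures can be recorded only among 59 − m patients, so the error is P(X ≤ 4; n = 59 − m, p = 0.15):

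| m | 0 | 1 | 2 | 3 | 6 | 9 | 12 |
|---|---|---|---|---|---|---|---|
| type I error | 0.047 | 0.052 | 0.057 | 0.063 | 0.085 | 0.112 | 0.147 |

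One unobserved patient is enough to exceed 0.05.

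**3. Each patient unobserved with probability q, unrelated to outcome.** The recorded failure rate becomes 0.15 × (1 − q), and the error is P(X ≤ 4; n = 59, p = 0.15(1 − q)):

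| q | 0 | 5% | 10% | 20% |
|---|---|---|---|---|
| type I error | 0.047 | 0.064 | 0.086 | 0.149 |

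**4. The same point through the confidence bound.** The exact (Clopper-Pearson) one-sided 95% upper bound for 4 failures is 14.85% of 59, 15.1% of 58 and 16.4% of 53. Only the first lies below 15%.

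**5. Cut-off and power when only patients with known status are used.** The bound lies below 15% exactly when P(X ≤ x; n, 0.15) < 0.05:

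| known n | failures allowed | type I error | power at 5% |
|---|---|---|---|
| 59 | 4 | 0.047 | 0.828 |
| 58 | 3 | 0.019 | 0.670 |
| 56 | 3 | 0.024 | 0.693 |
| 53 | 3 | 0.033 | 0.727 |

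**6. Every unknown counted as a failure.** Power at a true 5% rate is P(X ≤ 4 − m; n = 59 − m, p = 0.05): 0.670 for m = 1, 0.453 for m = 2 and 0.223 for m = 3.

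**7. Why the choice of bound matters.** A Wald upper bound with all 59 known would accept 5 failures: 5/59 = 0.0847, standard error √(0.0847 × 0.9153 / 59) = 0.0363, upper bound 0.0847 + 1.645 × 0.0363 = 0.144. The error would then be P(X ≤ 5; 59, 0.15) = 0.106. That is worse than 10% unobserved under the present rule (0.086).

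**The case against.** Several points on the other side have force.

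- **The protocol nowhere says that lost patients count as non-failures.** That is so. It follows from the denominator and from the absence of any other rule. Handling of missing status is often left to an analysis plan, but here the protocol does not leave it open. It asserts that follow-up is complete and builds the estimator on that assertion.
- **Follow-up is intended to be thorough.** Section 7.0 has all patients seen every 3 months for 2 years. Section 5.9 brings externally treated patients to the lead centre for oncology follow-up and imaging. Section 3.0 treats surgery as part of the pathway, and 6.6 records its type and margins. A patient who has surgery is therefore not necessarily lost. The censoring wording in 6.2 is standard, and the wording in 8.0 concerns scan-based endpoints. Neither predicts how much loss occurs within two years. This limits the likely size of the problem, but 4.4 still speaks of leaving the trial, and nothing requires local status to be collected afterwards.
- **Final analysis waits until everyone has two years.** That removes administrative censoring. It does not recover a patient who has left.

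A reader might go further and make three inferences that the documents do not support:

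- **That deaths bias the endpoint.** A death with local failure known to be absent is properly a non-failure. A cumulative incidence with death as a competing event treats it in the same way. Only death with local status unknown belongs to this concern.
- **That patients who leave for surgery are the likeliest to develop unsalvageable disease.** This may be so, but the protocol gives no such rate. If loss did follow poor response, the error would be higher than shown.
- **That the 5% error is already broken.** It is exceeded only if at least one patient is in fact unobserved.

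**Conclusion.** The concern holds as a conditional statement. The protocol states a premise that its own sections 4.4, 6.2 and 8.0 do not support. It rests a pass/fail count on that premise, with no allowance for loss in the recruitment target. If follow-up is complete, nothing is wrong and the error is 4.7%. One unobserved patient takes it to 5.2%, and assumed losses of 5%, 10% and 20% take it to 6.4%, 8.6% and 14.9%. These figures assume that loss is unrelated to outcome, that unknown patients are counted as non-failures, and that the true rate is at the 15% limit. Because the endpoint carries the safety claim and the slack is less than one patient, the text should be corrected.

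**What to change.** 1. In 8.0, delete the premise of complete follow-up.
2. In 4.4 and 8.0, state that a patient who withdraws from deferral or has surgery stays in follow-up for local status to two years, unless consent is withdrawn.
3. Count a patient as a non-failure only if local status is known at two years, or up to death if death comes earlier.
4. Judge the endpoint by the exact (Clopper-Pearson) one-sided 95% upper bound, which must lie below 15% among patients with known status. With 59 known this is the present 4-of-59 rule; with 58, 56 or 53 known it allows 3 failures.
5. Report a sensitivity analysis that counts every unknown as a failure. It should be supportive and not decisive, because one unknown would already cut power to 0.67 and three to 0.22.
6. A cumulative-incidence estimate with death as a competing event may be added as support. A Wald bound on it should not be the decision rule, because it would pass 5 of 59.

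**Cost:** a few lines of text, and collection of local status after surgery or withdrawal, largely through visits already planned. If patients are truly lost, power at a true 5% rate falls from 0.83 to about 0.67–0.73 for 58 to 53 known. Restricting the analysis to known status still assumes that loss is unrelated to outcome, which is why item 5 is needed.

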3.0 STUDY OBJECTIVES

The primary objective of this study is to establish the time to maximum tumour response following CRT, and to investigate whether surgery can be safely avoided within the tight framework of the trial follow-up protocol in a small group of patients where the cancer becomes undetectable by imaging modalities.

It also allows the use of 18F-FDG PET/CT in combination with MRI and clinical examination (tri-modality assessment) to assess for a continued incremental response to CRT. It should be made clear that surgery is not withheld from patients entering this study. Indeed, surgery is an option at each stage of patient follow-up and is a crucial component of a patient's treatment pathway if a point is reached when there is no further regression of disease. However, should the patient refuse surgery or be medically unfit for a rectal surgery, they will continue to be followed up without surgical intervention. If a status of 'no detectable disease' by serial MRI, PET/CT and clinical assessment is achieved and the patient wishes not to have surgery, they will continue to be stringently monitored within the framework of the trial follow-up protocol.

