Progression free survival will be measured as time until the first occurrence of any of the following: increased Mandard grade (in patients who did not achieve CR), any tumour T1 or above (in patients who achieved CR), first diagnosis of nodal or distant disease (diagnosed on MRI, CT, PET or pathology); or death from any cause.

Quality of life will be measured using EORTC QLQ-C30, IBDQ and Vaizey questionnaires. Missing data will not be replaced, but numbers assessed at each time-point will be reported. Change from baseline will be assessed at each time-point and summarised using descriptive statistics. In addition, counts and percentages of LENT-SOMA worst grades at each time-point will be reported.

Sample size

We wish to show that the percentage of patients who can successfully omit surgery is at least 10%, with a true rate expected to be at least 25% (and possibly this may be considerably higher). The two-year failure rate is assumed to be no more than 5%, and a failure rate of 15% or more would be considered to be unacceptable.

Using a single-stage exact phase II design, with one-sided significance level of 0.05, then a total of 59 patients would provide 80% power to prove a 2-year failure rate of less than 15% if the true rate is no more than 5%. The trial would be a success according to this endpoint if no more than 4 patients out of 59 have local failure at 2 years. The same number of patients would provide at least 90% power to show that the proportion of patients safely omitting surgery is more than 10%, if the true rate is

expected to be at least 25%. The trial would be a success according to this endpoint if at least 11 out of 59 patients have safely omitted surgery. To be judged a success overall the trial must pass both of these endpoints (no more than 4 patients with local failure, and at least 11 safely omitted surgery).

We expect to recruit 39 patients from the Royal Marsden and network hospitals and 20 patients from other multi-centre sites. This recruitment is expecting to be completed by 31st December 2012. We believe 60% of eligible patient will wish to participate in the "deferral of surgery". However, only 20% of rectal patients who undergo pre-operative CRT will develop a complete response and meet the inclusion criteria.

Stopping Rule

The trial will be stopped if 5 patients develop disease which is surgically not

salvageable or incompletely excised. There will be continuous monitoring of all

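### Protocol 3.1 and 8.0 define the first primary endpoint differently: 3.1 requires complete response, while the 8.0 analysis sentence asks only for continued response without surgery

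*Protocol*

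**What the plan says.** Section 3.1 sets the first primary endpoint, and opens with the aim and the time point: "To estimate the percentage of patients who can safely omit surgery, defined as the percentage of patients at two years after end of CRT". It then restricts the count to those "who have not had surgery and who are in CR (no detectable local disease"). Two conditions must both hold: no operation, and complete response.

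Section 8.0, under its heading for the primary endpoints, states what will be computed. It is "the percentage of patients in continued response without surgery at two years", taken over all patients, with an exact 95% binomial interval. CR is not mentioned in that sentence, and *continued response* is not defined anywhere in the protocol.

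The sample-size text in 8.0 uses further wording for the same endpoint. The hypothesis is that "the percentage of patients who can successfully omit surgery is at least 10" per cent. The success rule requires that "at least 11 out of 59 patients have safely omitted surgery".

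Section 3.0 says of patients who do not go to surgery: "should the patient refuse surgery or be medically unfit for a rectal surgery, they will continue to be followed up without surgical intervention". No CR condition is attached to that statement.

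**The concern.** In this protocol response and complete response are not the same thing. Section 4.0 treats complete and partial response as separate RECIST categories, and the trial enrols partial responders. A patient who declines or is unfit for surgery and still has residual tumour at two years, without regrowth, is not a success under 3.1. The same patient can be read as a success under the 8.0 analysis sentence.

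At stake is what the headline result means. A percentage reported as surgery safely omitted could include patients with tumour still present whose operation was omitted because they refused it or could not have it. The choice between the two wordings could also be made after the counts are known, and it could decide whether the endpoint passes.

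**Working it through.** **1. The plan's own figures.** Inputs from the sample-size text in 8.0: n = 59, null rate 10%, expected rate 25%, one-sided level 0.05, success at 11 or more. With X ~ Binomial(59, p):

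- P(X ≥ 11 | p = 0.10) = 0.0306, within 0.05. A cut-off of 10 would give 0.0666, so 11 is the right cut-off.
- P(X ≥ 11 | p = 0.25) = 0.9028, which agrees with the stated power of at least 90%.
- For endpoint 2, P(X ≤ 4 | p = 0.15) = 0.0469 and P(X ≤ 4 | p = 0.05) = 0.8281, which agree with the stated level of 0.05 and power of 80%.

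The design figures are sound. The question is only which event is counted.

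**2. Can the two wordings give different counts?**

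- Partial responders enter the trial: 4.0 admits TRG 2 on MRI, and 4.1 (g) admits partial response with further incremental response.
- On the pathological scale described in 2.6, TRG 2 means that some residual cancer cells remain.
- The stable-disease rules in 4.4 (b) and 7.0 apply only to disease that has not reached TRG 1 or 2. Neither rule removes a patient with stable TRG 2.
- Section 3.0 keeps patients who refuse or are unfit for surgery in unoperated follow-up.
- Endpoint 2 does not catch these patients. Section 3.1 defines local failure as surgically unsalvageable disease, so a stable, resectable residual tumour is not a failure there.

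Such patients are therefore possible. The protocol does not say how many to expect.

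**3. Size, if the broader wording were used for the count.** Each such patient adds 1/59 = 1.7 percentage points to the reported rate. Ten CR patients (10/59 = 16.9%) miss the rule; ten plus one unoperated partial responder (11/59 = 18.6%) meet it.

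Let k unoperated patients with residual disease be counted (k is an assumption), and let the other 59 − k each be unoperated and in CR with probability 0.10. The pass probability is P(Y ≥ 11 − k), with Y ~ Binomial(59 − k, 0.10):

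| k | Pass probability, endpoint 1 |
|---|---|
| 0 | 0.0306 |
| 1 | 0.0605 |
| 2 | 0.1120 |
| 3 | 0.1934 |
| 4 | 0.3096 |
| 5 | 0.4575 |

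One such patient is enough to exceed 0.05.

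Alternatively, hold the CR-without-surgery rate at 10% of all patients and add a proportion x of unoperated partial responders (also an assumption). Then P(X ≥ 11 | 59, 0.10 + x) is 0.2648 for x = 0.05 (59 × 0.05 = 2.95 patients expected), 0.6536 for x = 0.10 and 0.9028 for x = 0.15.

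**The case against.** The strongest reply is that the decision rule does not use the loose phrase. It is written in terms of safely omitting surgery, which 3.1 defines by CR, and the power statement uses the same term: "at least 90% power to show that the proportion of patients safely omitting surgery is more than 10" per cent. Read by its defined term, the rule already excludes patients with residual disease. This stands. A reader might infer that the success rule itself admits such patients, or that the 10% null is tested on the wrong event. The documents do not support either inference. Both would follow only if the analysis sentence were taken as the operative definition.

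It can also be said that *continued response* is shorthand for sustained complete response. Section 2.4 and the MRI discussion in section 2 describe the goal in those terms, and the same analysis sentence also leaves local failure to be defined in 3.1. Section 8.0 lists continued stable disease as a category in its own right, so an unchanged residual tumour might not be called a response at all. That reading is possible but not secured. Section 5.9 uses continued incremental response as something different from having no visible disease, and 8.0 names CR elsewhere when it means CR.

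The affected group may be small. The stable-disease rules narrow it mainly to persistent TRG 2 and to patients who refuse or are unfit for surgery. The pass probabilities above rest on assumed numbers and concern endpoint 1 alone. Overall success also needs no more than four local failures, so they are not the chance of a false success for the trial.

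A statistical analysis plan, not at hand here, could choose one wording. That would not cure the protocol, which states the event in two ways and would allow either choice.

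**Conclusion.** The inconsistency is real and concerns a pass/fail primary endpoint. Section 3.1 and the success rule, read through 3.1, require CR. The sentence in 8.0 that produces the percentage and its interval does not. As written, the reported estimate follows the broader phrase. The success count could follow it as well, but the text does not say that it does.

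If it did, the chance of passing endpoint 1 with a 10% CR-without-surgery rate among the other patients would go from 0.0306 to between 0.0605 and 0.1934 with one to three such patients counted. This is conditional on the broader reading and on an assumed number of patients. The sample size, cut-offs, level and power in 8.0 are not in error.

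**What to change.** In the primary-endpoints paragraph of 8.0, replace the continued-response phrase with the 3.1 event: patients "who have not had surgery and who are in CR (no detectable local disease") at two years after the end of CRT, as a percentage of all patients. Use that one term throughout 8.0, including the confidence interval, the 10% and 25% rates and the 11-of-59 rule. The proportion in continued response without surgery may still be reported descriptively, labelled as a different quantity.

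Copying 3.1 is enough. Extra conditions that 3.1 does not state, such as being alive or limiting surgery to rectal cancer surgery, would be a separate change and should not be presented as part of the existing definition.

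The cost is one sentence and consistent terminology. N = 59 and both cut-offs are unchanged, and clinical management is not touched. The downside is a possibly lower reported rate of surgery omitted.

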5.5 Molecular prognostic and predictive markers of response	
to treatment substudy	15
5.6 Toxicity	16
5.7 Duration of Treatment	17
5.8 Pre-Registration Evaluation	17

5.9 Consenting Process	17
5.10 Adjuvant Chemotherapy	17
5.11 Adverse Events	18
5.11.1 Adverse events not subject to reporting	18
5.12 End of Trial Definition	18
	10
6.0 Assessment of Efficacy	18
6.1 Local Recurrence/Tumour regrowth	. 18
6.2 Overall Survival	19
6.3 Disease-free Survival	19
6.4 Quality of Life	19
6.5 Time to maximum tumour response	19
6.6 Rectal Surgery	19

7.0 Follow Up	19
8.0 Statistical Considerations	21
9.0 References	23
 10.0 Appendix. 10.1 Response Evaluation Criteria in Solid Tumours. 10.2 Modified Mandard Tumour Regression Grade. 10.3 PET/CT Central review. 10.4 MRI Method / Data Sheet . 10.5 Follow-Up Schedule. 10.6 LENT-SOMA. 10.7 FOPTC OOL 	25 25 26 27 43 51 53 57
10.7 Eok TC QOL 10.8 Vaizey Incontinence Questionnaire 10.9 MIBDQ	59 60

Fig. 1 'DEFERRAL OF SURGERY' TRIAL OUTLINE

- Rectal Cancer (T3/4, low T2 with threatened CRM, any N, M0)
- No pelvic side wall disease
- No local recurrence
- No metastatic disease
- Imaged on MRI

¥ Patients who have had am MRI performed more than 4 weeks following completion on CRT can also be included, with the next MRI/18F-FDG PET/CT scheduled 4 weeks afterwards. 18F-FDG PET/CT will be performed at 8 weeks, 16 weeks and 1 year following completion of CRT

* 'partial response' and stable disease' are defined by the RESCIST criteria, appendix 10.5

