2.5 MRI as a tool assess response to Preoperative Chemo-Radiotherapy

The accuracy of high-resolution MRI in predicting the presence or absence of tumour at the surgical circumferential resection margin of the rectal cancer specimen has been prospectively investigated by the MERCURY group from the Pelican Cancer Foundation^{15,16}. 408 consecutive patients from 12 colorectal units in 4 European countries with all stages of rectal cancer underwent MRI prior to TME. Specificity for prediction of a clear circumferential resection margin by magnetic resonance imaging was 92% (327/354, 95% CI: 90-95%).

MRI is also a useful tool for assessing tumour response to CRT for rectal cancer. This has been prospectively evaluated at the Royal Marsden Hospital by the same Consultant Radiologist interpreting serial MRIs in this study¹⁷. 25 patients with poorrisk adenocarcinoma of the rectum treated with neo-adjuvant chemoradiation underwent MRI imaging before and after chemoradiation treatment and were independently reviewed in consensus by 2 expert radiologists to determine the tumour stage, nodal size, nodal distribution and nodal stage. Total mesorectal excision surgery after chemoradiation 152 mesorectal nodes were visible and 4 of 52 malignant nodes were in contact with the mesorectal fascia. After CRT, only 29 nodes were visible and none were in contact with the mesorectal fascia. Nodal downstaging was observed: 20/25 N0 and 5/25 N1 (p<0.01). The results of this study demonstrates downsizing and downstaging of the primary rectal tumour after CRT with good agreement between MRI and pathologic T and N staging.

The Imaging Principle Investigator has developed a detailed post chemoradiotherapy (CRT) MRI specific tumour response grading (MRI TRG) for rectal cancer generated from the experience gained from the following clinical trials:

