6.0 ASSESSMENT OF EFFICACY

6.1 Local Recurrence Rate / Tumour Re-growth

Local recurrence rate in patients who have achieved a sustained clinical and radiological complete response will be measured from the end date of CRT to time of documentation of local tumour recurrence/regrowth. It is emphasized that the development, or progression, of metastatic disease does not constitute local failure.

Time to Tumour regrowth / tumour recrudescence in patients who have not achieved a sustained clinical and radiological complete response will be measured from the date of start of CRT to time of documentation of tumour regrowth.

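### Section 8.0 classes nodal disease as distant without separating mesorectal nodes, so node-only regrowth in the mesorectum is recorded as distant disease and not as local regrowth

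*Protocol*

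**What the plan says.** Section 8.0 of the protocol defines the distant endpoint: "Time to distant disease will be measured as the time to the first diagnosis of lymph node or other distant disease". MRI is among the accepted means of confirmation, and no nodal station is named or excluded.

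The local endpoint, in the same section, reads: "Time to local regrowth will be measured as the time until the first recorded increase in Mandard grade, on MRI". It has no nodal component. Its censoring rule adds: "Patients who opt for surgery or withdraw for other reasons before recorded local regrowth will be censored at date of last scan".

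Other places word the matter differently:

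- The progression-free survival definition in 8.0 lists "first diagnosis of nodal or distant disease (diagnosed on MRI, CT, PET or pathology", which names nodal and distant disease as two things.
- Section 6.1 measures local recurrence "to time of documentation of local tumour recurrence/regrowth", with no reference to Mandard grade or to nodes. It adds that "the development, or progression, of metastatic disease does not constitute local failure".
- The trial outline (Fig. 1) describes the population as "Rectal Cancer (T3/4, low T2 with threatened CRM, any N, M0", so nodal stage and metastatic stage are kept apart there.
- Section 3.1 defines primary endpoint 1 as no surgery and complete response at two years, glossed as the absence of detectable local disease. It does not say whether mesorectal nodes are local.

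**The concern.** The trial asks whether surgery can be safely deferred or avoided. Deferral leaves the mesorectum and its nodes in place. If disease regrows in one of those nodes while the primary site still looks good, that is a local cost of not operating. A reader will take distant disease as spread that pelvic surgery would not have prevented, and local regrowth as the price of deferral. A definition that puts mesorectal nodes in the first category makes local control look better than it is and distant spread look worse.

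The censoring rule adds to this. A patient operated on because of a node-only regrowth, before any rise in Mandard grade, leaves the local-regrowth analysis as a censored observation. Kaplan-Meier estimation treats such a patient as having the same future risk as those still followed, although the patient left because disease had come back in the pelvis.

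**Working it through.** **Step 1. Follow one patient through the definitions.** Take a patient whose Mandard grade is unchanged and in whom a mesorectal node regrows on MRI after the end of chemoradiotherapy.

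| Endpoint | Where defined | How the patient is recorded |
|---|---|---|
| Time to distant disease | 8.0 | Event |
| Time to local regrowth, no surgery | 8.0 | No event |
| Time to local regrowth, surgery follows | 8.0 | Censored at last scan |
| Local recurrence | 6.1 | Not settled; the wording could include the node |
| Progression-free survival | 8.0 | Event, under either label |
| Primary endpoint 2 (surgically unsalvageable disease) | 3.1 | Depends on salvageability, not on the label |
| Primary endpoint 1, surgery within two years | 3.1 | Not a success, under either label |
| Primary endpoint 1, no surgery | 3.1 | Not settled |

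If the Mandard grade rises as well, local regrowth is recorded in addition to distant disease. The misclassification is limited to node-only regrowth.

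**Step 2. Check that the design figures are untouched.** Inputs from 8.0: N = 59, one-sided 0.05; local failure 15% against 5%, success at 4 or fewer; omission of surgery 10% against 25%, success at 11 or more. Exact binomial:

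- P(X ≤ 4 | 59, 0.15) = 0.0469 and P(X ≤ 4 | 59, 0.05) = 0.828. This agrees with the stated 0.05 and 80%.
- P(X ≥ 11 | 59, 0.10) = 0.0306 and P(X ≥ 11 | 59, 0.25) = 0.903. This agrees with the stated 0.05 and at least 90%.

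The plan's figures reproduce, and none of them uses the definition of distant disease or of local regrowth.

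**Step 3. Size.** As a crude proportion, one reclassified patient is 1/59 = 1.7 percentage points taken from local regrowth and added to distant disease.

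The protocol gives neither a regrowth rate for this cohort nor the share that is node-only, so any total is an assumption. Let R be the true locoregional regrowth rate and s the node-only share. Patients moved = 59 × R × s; recorded local regrowth = R × (1 − s).

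| R (assumed) | s (assumed) | Patients moved | Recorded local regrowth |
|---|---|---|---|
| 20% | 5% | 59 × 0.20 × 0.05 = 0.6 | 19% |
| 30% | 20% | 59 × 0.30 × 0.20 = 3.5 | 24% |
| 40% | 30% | 59 × 0.40 × 0.30 = 7.1 | 28% |

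The range is wide because the inputs are unknown. It shows the direction and scale and is not an estimate.

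**The case against.** The best defence is grammatical. The phrase in 8.0 can be parsed so that distant governs both parts: distant disease in lymph nodes or at other sites. The progression-free survival wording shows that the authors do distinguish nodal from distant. On that reading mesorectal nodes are unassigned rather than misassigned. This is possible but not the natural reading, because the words as written make nodal disease one kind of distant disease and accept MRI as confirmation. Even on the kinder reading, 8.0 gives a node-only mesorectal regrowth no place under local regrowth.

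Section 6.1 is looser than 8.0 and could be read to include mesorectal nodes. That stands. It means the two sections must be reconciled, and that it would be too strong to say the protocol never treats such regrowth as local.

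A reader might infer that primary endpoint 1 counts regional failures as successes. The documents do not support that. A patient who goes on to surgery fails the endpoint however the node is labelled, and section 7.0 sends radiological local recurrence to the surgical team at once. Section 3.0 describes the non-surgical group as free of detectable disease on MRI, PET/CT and clinical assessment, and section 4.0 ties complete response to the RECIST criteria of Appendix 10.1. Only the unoperated patient with isolated nodal disease is left unclear.

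A reader might also take a rate from the cited series. Section 2.5 reports "Nodal downstaging was observed: 20/25 N0 and 5/25 N1 (p<0.01", and 0.20 × 59 = 11.8 patients. That series was of poor-risk patients not selected for good response, whereas this trial enrols only good responders. Section 2.6 cites 91% node-negative among the two best regression grades, so 9%, or 0.09 × 59 = 5.3 patients, had involved nodes. That is pathology at resection, not regrowth during follow-up. Neither figure transfers.

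Lastly, Appendix 10.2, which defines the modified Mandard grade, was not in the text available. The body of the protocol describes the grade as a measure of the tumour, so a nodal component is unlikely but cannot be excluded.

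**Conclusion.** The point holds for two secondary endpoints. As 8.0 is written, node-only mesorectal regrowth after the end of chemoradiotherapy is a distant event and not a local one, and surgery before a grade rise turns it into a censored observation for local regrowth. The bias has a known direction: the incidence of local regrowth is too low and that of distant disease too high, by 1.7 percentage points of 59 per patient. The number of such patients cannot be derived from the protocol.

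It would be tempting to set a shift of several patients beside the 5% versus 15% contrast on which the trial is sized. That contrast concerns surgically unsalvageable disease, which this wording does not move. No decision rule, cut-off or power figure changes, and progression-free survival captures the event either way. For primary endpoint 1 there is an ambiguity, not a demonstrated miscount. The conclusion assumes that the natural reading of 8.0 is the one applied and that the Mandard grade has no nodal component.

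**What to change.** 1. In 8.0, limit distant disease to non-regional nodes and other metastases.
2. In 8.0, count new or progressing mesorectal nodal disease after the end of chemoradiotherapy, on MRI, PET/CT, CT or pathology, as locoregional regrowth alongside a rise in Mandard grade. Requiring new or progressing disease also settles how nodes already visible at entry are handled. Surgery after such an event then follows an event and is no longer a reason for censoring.
3. Use the same definition in 6.1, and use the same terms in the progression-free survival definition.
4. In 3.1, state that the absence of detectable local disease includes the mesorectal nodes.

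The cost is endpoint wording. Section 5.9 already provides for central review of all MRI, PET/CT and CT, so no new data are needed. The sample size and cut-offs stay as they are. The local regrowth figure may become slightly less favourable.
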